7.4.2. Interaction Analyses

Each of the three Primary Endpoints will be assessed for its association with various lead, procedural and subject characteristics. The interaction between each characteristic and stiffness will be assessed using a general linear model. Each characteristic will be assessed separately. The list of characteristics includes, but is not limited to:

Product Level Characteristics

- Model/serial of pulse generator and leads
- Lead related information:
 - Septal / apical positioning of lead
 - Active / passive fixation
 - Dual / single coil defibrillator lead
 - Manufacturer
 - Implant date(s) of leads
- Pulse generator information:
 - Implant date of pulse generator

- Manufacturer
- Pulse generator position

Implant Procedure Related Characteristics

- Access technique (axillary, cephalic, subclavian intra-thoracic, subclavian extra-thoracic)
- Lead configuration determined from retrospective AP/PA Chest X-rays collected post implant

Subject Level Characteristics

- Subject birth date, gender, race, ethnicity, height, weight
- Ejection fraction, implant indication

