Study Design and Objective(s)	
The AAMI Human Use Condition Study (HUCS) is a prospective, observational, multi-center clinical study intended to determine whether Right Ventricular (RV) lead curvature in vivo is a function of lead stiffness. The results of this study will comprise a reference dataset to be used in a new international standard for conductor flexural fatigue performance of implantable CIED (Cardiac Implantable Electrical Device) RV leads.
 
The HUCS study objectives are as follows:
 
 1. Measure dynamic in vivo curvature of RV pacing and defibrillator leads in the extravenous and intracardiac anatomy 2. Measure the relationship between lead bending stiffness and in vivo curvature 3. Assess the relationship between subject and implant variables and lead curvature
Primary Endpoints	
Three primary endpoints will assess the relationship between lead stiffness and curvature – one endpoint each for three different regions of the lead.
 
 1. In vivo cyclic curvature and mean curvature of pacing and defibrillation leads in the extravenous region will be determined during specified arm movements. 2. In vivo cyclic curvature and mean curvature of pacing and defibrillation leads in the intracardiac region will be determined during two or more cardiac cycles. 3. In vivo cyclic curvature and mean curvature of pacing and defibrillation leads in the connector region will be determined during specified arm movements. 
The relationship between lead stiffness and curvature will be evaluated for all three Primary Endpoints.

Subject Population	
The study will enroll at least 80 and up to 120 subjects with one of four different market-released lead families identified in the tables below.

	The leads are from all four CIED manufacturers participating in this protocol. Approximately 30 leads from each manufacturer's lead family will be required.		
ICD Leads of Interest	Manufacturer	Model(s)	Description
	Abbott	LDA 210Q LDA 220Q LDA 230Q	Optisure Single Coil Defibrillation Lead Optisure Dual Coil Defibrillation Lead Optisure Dual Coil Defibrillation Lead
	Medtronic	6935M	Quattro Secure Single Coil Defibrillation Lead
Pacing Leads of Interest	Manufacturer	Model(s)	Description
	Biotronik	Siello S, Solia S	Active Fixation Leads

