7.4.3. Multivariable Analyses

The association between curvature and stiffness will be evaluated in the presence of other potential confounding variables, including but not limited to the characteristics listed above. A multivariable general linear model for each endpoint will be analyzed, treating curvature as the outcome and stiffness and other characteristics as the predictors. To minimize the potential for overfitting the multivariable model, a subset of characteristics will be included in the model. To select which characteristics are included in the multivariable model, each characteristic's association with curvature will be assessed via a univariable model. Characteristics significantly associated with curvature in the univariable models will be included in the multivariable model. A separate multivariable model will be analyzed for each endpoint.

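### Section 7.4.2 promises an association analysis but names only an interaction test, and the screen in 7.4.3 that partly covers Objective 3 is not adjusted for stiffness

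*Combined protocol and SAP*

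**What the plan says.** The third objective in the protocol synopsis is to "Assess the relationship between subject and implant variables and lead curvature".

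Section 7.4.2 (Interaction Analyses) opens in the same spirit: "Each of the three Primary Endpoints will be assessed for its association with various lead, procedural and subject characteristics". It then specifies one test: "The interaction between each characteristic and stiffness will be assessed using a general linear model". On how the characteristics are handled it adds "Each characteristic will be assessed separately". It gives no significance level, and it does not say whether the model also contains the characteristic's main effect or whether stiffness is centred.

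Section 7.4.3 (Multivariable Analyses) has a different stated purpose: "The association between curvature and stiffness will be evaluated in the presence of other potential confounding variables". To choose covariates, "each characteristic's association with curvature will be assessed via a univariable model", and then "Characteristics significantly associated with curvature in the univariable models will be included in the multivariable model". The final model is described as "treating curvature as the outcome and stiffness and other characteristics as the predictors". The outcome named there is curvature, whereas the primary models in 7.2 use log(curvature). No level is given for the screen, and neither section says which analysis answers Objective 3.

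**The concern.** Objective 3 is a main-effect question: does a patient or implant factor go with higher or lower curvature? An interaction test asks something else, namely whether the stiffness slope differs between levels of the factor. A factor that moves log(curvature) by the same amount on soft and stiff leads satisfies the interaction null exactly, however large its effect.

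The univariable models in 7.4.3 do ask about association, but without stiffness. If levels of a factor differ in lead stiffness, the univariable coefficient mixes the factor's own effect with the stiffness effect that the study expects to find. Such links are plausible here. In Section 5, passive fixation is listed only for one pacing manufacturer and dual coil only for one defibrillation manufacturer. Indication and ejection fraction may well follow pacing versus ICD. The documents give no stiffness values, so the strength of any link is unknown.

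The results are to form a reference dataset for a lead standard. An implant factor wrongly passed over, or credited with an effect that belongs to stiffness, would carry into it.

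**Working it through.** **Inputs from the plan (7.3).** Thirty enrolled per family, at least 20 usable, 33% missing, one-sided alpha 10%, power 99%. The enrolment figure reproduces: 20/0.67 = 29.9, rounded up to 30, and 4 × 30 = 120. Usable leads: 4 × 20 = 80. The 99% power cannot be reproduced, because the residual SD of log(curvature) and the spread of stiffness are not given.

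**Assumptions.** Residual SD 1. The stiffness slope is scaled so that 80 leads give the plan's 99% power at one-sided 10%: noncentrality 3.627, and 3.627/√80 = 0.406 residual SD per SD of stiffness, negative in sign. The characteristic is binary, split 50/50, and shifts log(curvature) by 0.7 residual SD at every stiffness. Tests are two-sided 5%.

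**Interaction test (7.4.2).** The true interaction is zero, so the rejection rate is the test level. Simulation with both main effects in the model gave 4.8% to 5.1% for shifts of 0.5 to 1.0 SD, at 80 and at 120 leads. At a 10% level it gave 9% to 10%. More leads do not help.

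**Characteristic unrelated to stiffness.**
- Adjusted main effect: noncentrality 0.7 × √80/2 = 3.13, power about 87%.
- Univariable (7.4.3): the stiffness effect joins the error, so the SD is √(1 + 0.406²) = 1.079. Noncentrality 3.13/1.079 = 2.90, power about 82%.
- Loss: 87 − 82 = 5 points. For shifts of 0.5 and 1.0 SD the pairs are 53% against 60% and 98% against 99%.

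**Correlation 0.5 with stiffness, either direction.** For a 50/50 split this means that the two levels differ by 1 SD in mean stiffness, with within-level stiffness variance 0.75.
- Adjusted main effect: 3.13 × √0.75 = 2.71, power about 76% in both directions.
- Univariable SD: √(1 + 0.406² × 0.75) = 1.060.
- Univariable, effects offsetting: net shift 0.7 − 0.406 = 0.294; noncentrality 0.294 × 4.472/1.060 = 1.24, flagged about 23%.
- Univariable, effects reinforcing: net shift 0.7 + 0.406 = 1.106; noncentrality 1.106 × 4.472/1.060 = 4.67, flagged over 99%. The estimate is then too large, because 0.406 of it belongs to stiffness.

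| Scenario (0.7 SD shift, 80 leads) | Interaction | Univariable | Adjusted |
|---|---|---|---|
| Unrelated to stiffness | about 5% | 82% | 87% |
| Correlation 0.5, offsetting | about 5% | 23% | 76% |
| Correlation 0.5, reinforcing | about 5% | over 99% | 76% |

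**If the interaction model omits the main effect.** Section 7.4.2 does not rule this out. With stiffness uncentred (mean assumed 3 SD above zero), the product term absorbs the shift. A 0.5 SD parallel shift was then flagged in 55% of simulated datasets of 80 leads and would be reported as a difference in slope.

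**The case against.** The strongest reply is that 7.4.3 already tests every characteristic against curvature, and that those passing the screen enter a model with stiffness. Objective 3 does not ask for an effect at a given stiffness. This largely stands. A reader might infer from 7.4.2 alone that Objective 3 goes unanswered, or that the plan's power for a parallel shift falls from 87% to 5%. The documents do not support either reading: when the characteristic is unrelated to stiffness, the plan taken as a whole loses about 5 points.

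A reader might also infer that no routinely fitted model can give a stiffness-adjusted effect. That does not follow. If the 7.4.2 model contains stiffness, the characteristic and their product, the effect at mean stiffness can be read from it with the same power as the adjusted model (87%, or about 76% at correlation 0.5). The difficulty is that 7.4.2 neither says that the model has this form nor asks for that estimate.

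Nor does the plan say that a non-significant interaction will be reported as no association. The 0.5 correlation is assumed. These are additional analyses without a power claim, and Section 8.1.5 refers to a separate statistical analysis plan, not among the documents reviewed, which may settle coding and levels.

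What remains is that the 7.4.3 test is unadjusted, is there to pick covariates for the stiffness question, and leaves any characteristic that fails it without a reported adjusted effect.

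**Conclusion.** The point holds in a limited form. Within 7.4.2 the stated aim and the named test do not match, and that test has no power beyond its level for an equal shift at all stiffnesses. This result does not depend on the assumed SDs, only on both main effects being in the model. Section 7.4.3 covers Objective 3 in part: well for characteristics unrelated to stiffness, unreliably for those linked to it, where the effect can be hidden or inflated. The 23%, 76% and over-99% figures rest on the assumed slope scale, a 0.7 SD shift, a balanced binary characteristic, a 5% level and a correlation of 0.5. A weaker link would bring the univariable and adjusted results closer together. The primary endpoints are not affected. The change is worth making because it gives a stated objective a matching, less biased estimate from data already collected.

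**What to change.** In 7.4.2, and in the statistical analysis plan:

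1. For each endpoint and each subject or implant characteristic, fit log(curvature) = a × stiffness + b + c × characteristic + error. Report c with its confidence interval as the Objective 3 result, whatever the 7.4.3 screen shows.
2. Then add the product term, with both main effects in the model and stiffness centred at its study mean. Report it as a separate question about differences in slope, and state that a non-significant interaction is not evidence of no association.
3. State the significance level for these analyses, and use log(curvature) as the outcome in 7.4.3 as well.
4. Note that characteristics which largely define the lead family, such as manufacturer and lead model, may be collinear with stiffness, and report their adjusted estimates with that caveat.

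The cost is a few sentences and one extra exploratory regression per characteristic per endpoint. No new subjects, imaging or data are needed. The downside is a longer list of exploratory estimates.

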7.4.3. Multivariable Analyses

The association between curvature and stiffness will be evaluated in the presence of other potential confounding variables, including but not limited to the characteristics listed above. A multivariable general linear model for each endpoint will be analyzed, treating curvature as the outcome and stiffness and other characteristics as the predictors. To minimize the potential for overfitting the multivariable model, a subset of characteristics will be included in the model. To select which characteristics are included in the multivariable model, each characteristic's association with curvature will be assessed via a univariable model. Characteristics significantly associated with curvature in the univariable models will be included in the multivariable model. A separate multivariable model will be analyzed for each endpoint.

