4.1. Background

The implantable leads are the only elements of the implantable cardioverter-defibrillator (ICD) system that are meant to last the life of the patient without repair or replacement. However, survival of ICD leads may be as low as 85% after 5 years and 60% after 8 years.¹ Like all engineered systems, implantable leads are subject to degradation and possible failure from the effects of stresses imposed by the use environment. Conductor fracture caused by metal fatigue is one of the more serious and common failure mechanisms for transvenous ICD leads.

Fatigue life can be quantified in bench tests based on the stress-life method. In fatigue testing of ICD leads and in the *in vivo* use condition, conductor stress, σ , is proportional to curvature (C) and alternating stress, S , is proportional to cyclic (alternating) curvature (ΔC). For this reason, alternating stress, S , in lead fatigue studies is customarily reported as cyclic curvature with units of cm^{-1} or inch^{-1} .

To develop physiologically relevant bench tests for conductor fatigue performance of ICD and pacing leads, valid data on *in vivo* lead motion is needed - specifically cyclic curvature (ΔC) in the intracardiac, extravenous, and connector regions. Preliminary studies have demonstrated the feasibility of acquiring these data by 3D reconstruction of bi-plane cine fluoroscopy images.^{2 3 4} However, these studies were not randomized and did not control for effects of lead routing from the pulse generator implant site to the venous access site. None were powered to provide sufficient data for the purpose defined for the present study.

The stress-life (commonly denoted "S-N" in the literature on fatigue failure of materials) method was the first approach used to understand and quantify metal fatigue. It has been the standard design method for almost 100 years. The S-N approach is still widely used in design applications where applied stress is primarily within the elastic range of the material and the resultant lives (cycles to failure) are long, such as power transmission shafts.⁵

¹ Kleemann et al, Circulation 2007;115:2474-2480

² W Baxter, N Skadsberg, et. al., New Unanticipated Insights on Peak Lead Bending During Pectoralis Flexure. HRS 2010

³ Pau, W Baxter, et. al., Lead Use Conditions Imaging: A Noninvasive Upper Thoracic and Intracardiac Lead Mechanics Investigation, CARDIOSTIM, June2014

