7.2.1.1. Hypotheses

The following set of hypotheses will be used to evaluate the relationship between lead stiffness and curvature in the extravenous region:

$$H_0: a \geq 0$$

$$H_a: a < 0$$

[figure not shown]
where a represents the coefficient for stiffness in the following model:
 $\log(\text{curvature}) = a * \text{stiffness} + b + \text{normally distributed error.}$

Prior studies of in-vivo curvature have shown that a lognormal distribution models the data well. The alternative hypothesis represents an inverse relationship between lead stiffness and curvature.

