7.2.1.2. Statistical Methods

Each lead with lead stiffness and curvature data available in the extravenous region of the lead will be included in the analysis of Primary Endpoint 1. Each lead's curvature measurement used in the analysis will represent the maximum value of the curvature observed in the extravenous region. Each lead's stiffness measurement used in the analysis will represent the stiffness measurement at the location corresponding to the maximum value of the curvature (Figure 6).

Figure 6: Curvature and Stiffness Values used Primary Endpoint 1 Analyses

Arrows indicate maximum value for ΔC and corresponding stiffness for the extracardiac region.

The relationship between curvature and stiffness will be evaluated via a general linear model, treating log (curvature) as the outcome and stiffness as the predictor. The following model will be fit: $\log (\text{curvature}) = a * \text{stiffness} + b + \text{normally distributed error}$. The 90% upper confidence limit of the coefficient for stiffness, a , will be compared to 0. If the upper confidence limit is less than 0, the null hypothesis will be rejected, thereby establishing a significant relationship between curvature and stiffness in the extravenous region.

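### Section 7.4.3 names curvature, not log(curvature), as the outcome of the adjusted model, and gives lead-routing variables no guaranteed place in it

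*Combined protocol and SAP*

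**What the plan says.** Section 7.4.3, under Additional Analyses, sets its aim: "The association between curvature and stiffness will be evaluated in the presence of other potential confounding variables". The model is described as follows: "A multivariable general linear model for each endpoint will be analyzed, treating curvature as the outcome and stiffness and other characteristics as the predictors". To limit its size, "To minimize the potential for overfitting the multivariable model, a subset of characteristics will be included in the model", and the rule for choosing that subset is: "Characteristics significantly associated with curvature in the univariable models will be included in the multivariable model". No significance level is given and no characteristic is exempt. The only alpha in the document, one-sided 10% in section 7.3, is stated for the primary endpoints.

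The primary models are specified differently. Section 7.2.1.2 describes a general linear model "treating log (curvature) as the outcome and stiffness as the predictor", and 7.2.1.1 gives the reason: "Prior studies of in-vivo curvature have shown that a lognormal distribution models the data well". The intracardiac and connector endpoints use the same wording.

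On lead routing, section 4.1 says that earlier studies "did not control for effects of lead routing from the pulse generator implant site to the venous access site". Routing is not listed under that name in 7.4.2. The nearest items are access technique, pulse generator position and "Lead configuration determined from retrospective AP/PA Chest X-rays collected post implant".

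**The concern.** The study is observational and sets four manufacturers' lead families side by side. Section 7.4.3 asks whether the stiffness slope survives adjustment for other characteristics, and the results are meant to inform a standard. Two features weaken its answer.

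**Scale.** If the adjusted model is fitted to untransformed curvature, its slope is in curvature units per unit of stiffness. The primary coefficient a is a change in log curvature. Setting one beside the other would not show what adjustment did.

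**Selection.** A variable can confound the stiffness slope without being significant alone. If its effect opposes that of stiffness and the two are correlated, its marginal association is partly cancelled and the screen drops it. A confounder of moderate strength can also miss significance by chance. In the first case a real slope is understated. In the second, a slope can appear where stiffness has no effect.

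**Working it through.** **Plan's own figures.** 20/(1 − 0.33) = 29.85, so 30 enrolled per family, as section 7.3 states; 4 × 20 = 80 usable leads. The 99% power cannot be reproduced, because neither the residual SD nor the spread of stiffness is given. Working backwards with the noncentral t (n = 80, one-sided 10%), 99% power needs a standardised slope (|a| × SD of stiffness / residual SD) of 0.406. That value is used below.

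**Scale.** If log(curvature) = a × stiffness + b + normal error and stiffness is normal, the least-squares slope on raw curvature is a × mean curvature. With the plan's a = −0.23 and assumed means of 0.5, 1 and 2 cm⁻¹:

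- −0.23 × 0.5 = −0.115
- −0.23 × 1 = −0.23
- −0.23 × 2 = −0.46

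The raw slope can thus look half or twice a with no confounding present. This is a change of units, not a bias. Log and raw fits on the same data disagree on significance in 1.4 / 2.7 / 4.9 / 7.6% of 20,000 simulated studies at an assumed residual log-SD of 0.5 / 0.7 / 0.9 / 1.1.

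**Screen.** Assumptions: n = 80, log scale, one-sided 10% test of the slope, two-sided 5% screen, and a binary confounder split 40/40. At fixed stiffness its two groups differ by d residual SDs, and its correlation with stiffness is 0.3, 0.5 or 0.8. There were 20,000 runs per cell.

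The masking shows in the algebra. With the confounder coded ±1, its marginal coefficient in the opposing case is d/2 − 0.406 × correlation. At correlation 0.8 and d = 0.6 this is 0.30 − 0.325 = −0.025, so the screen rarely sees it. The unadjusted slope is then −0.406 + 0.8 × 0.30 = −0.166.

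Results for d = 0.2 / 0.4 / 0.6 / 0.8:

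| Case | Correlation | Plan's screen | Always included |
|---|---|---|---|
| Opposing, kept | 0.8 | 48 / 18 / 5 / 10% | 100% |
| Opposing, mean slope | 0.8 | −0.33 / −0.25 / −0.17 / −0.13 | −0.41 |
| Opposing, mean slope | 0.5 | −0.35 / −0.31 / −0.28 / −0.30 | −0.41 |
| Opposing, power | 0.8 | 84 / 76 / 56 / 36% | 80% |
| Opposing, power | 0.5 | 96 / 92 / 86 / 85% | 96% |
| Opposing, power | 0.3 | 95–98% | 98% |
| No stiffness effect, false rejection | 0.8 | 18 / 22 / 18 / 12% | 10% |
| No stiffness effect, false rejection | 0.5 | 15 / 16 / 14 / 11% | 10% |
| No stiffness effect, false rejection | 0.3 | 13 / 14 / 12 / 11% | 10% |

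With no adjustment at all, false rejection at correlation 0.8 would be 29 / 55 / 80 / 94%, so the screen removes most of the problem. A confounder acting in the same direction as a real stiffness effect causes little bias (mean slope −0.40 to −0.41).

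**Screen level.** At 10% or 20% instead of 5%, the worst false-rejection cell falls from 22% to 16% or 11%. At 20% every such cell lies between 10 and 12%. The opposing slope at correlation 0.8, d = 0.6 barely recovers: −0.17 becomes −0.18 or −0.21.

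**The case against.** **The outcome is probably log(curvature).** Section 7.4.3 fits a model for each endpoint, and each endpoint's model is on the log scale. Sections 7.2 and 7.4.1 also speak loosely of curvature. This is a fair reading, and a reader should not infer that the adjusted model will certainly be fitted to raw values. But 7.2 writes the log where it names the outcome, and 7.4.3 does not.

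**The separate SAP may settle it.** Section 8.1.5 cites one (AAMI_PC_WG1_N725), which is not among the documents reviewed and could state both scale and screening level. However, section 7.5 treats a departure from the protocol's analyses as a change needing a documented reason, so the protocol text should be right.

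**Routing is already examined in 7.4.2.** A reader might infer that lead routing goes uncontrolled throughout. The documents do not support that. Section 7.4.2 assesses each listed characteristic separately with stiffness, without a screen, and a masked confounder can show there. But 7.4.2 tests interactions one at a time and promises no adjusted slope, so the gap in the joint model remains.

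**The large effects need an extreme correlation.** This stands. No document figure supports 0.8 for access technique or generator position. At correlation 0.8 and d = 0.2, the screen even has more power than always including the confounder (84% against 80%), though with a biased slope.

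**Screening guards against overfitting.** That aim is sound. It justifies a small model, but does not require named confounders to pass a significance test.

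**Conclusion.** The point holds as a repair to an additional analysis that has no decision rule. It would be wrong to infer that the primary tests, their alpha or the sample size are compromised; none depends on 7.4.3.

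As written, the slopes before and after adjustment may be on different scales, and adjustment for lead routing in the joint model depends on a screen that can miss it. At correlations of 0.3 to 0.5 the effect on rejection rates is modest, although at 0.5 the mean slope can be understated by up to about a third (1 − 0.28/0.41 = 0.32). Serious loss of power appears only at 0.8 with the two larger effects.

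Residual SD, mean curvature, screening level, confounder strength and correlation are all assumptions, because the documents give none of them. The change is worth making before analysis, since scale, level and covariates should not be chosen after the data are seen.

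**What to change.** In section 7.4.3:

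- (a) State log(curvature) as the outcome of both the screen and the multivariable model. This is free.
- (b) Always include a short set fixed in advance: access technique and pulse generator position for the extravenous and connector regions, septal/apical lead position for the intracardiac region. Add lead configuration from chest X-ray in a sensitivity model, because the X-ray is provided only where available.
- (c) Keep the screen for all other characteristics and state its level. A lenient level such as 20% removes most of the excess false rejection, but not the bias from an opposing confounder.
- (d) Report the stiffness slope and its interval before and after adjustment, on the log scale and in the same subjects, with the number lost to missing covariates. Show any model with manufacturer or lead type as a labelled sensitivity model, since these may be nearly collinear with stiffness (an assumption; no stiffness values are given).

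No new data are needed. The costs are:

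- **Degrees of freedom.** Three for access technique (four categories) plus those for generator position, whose categories are not stated; one for the intracardiac region.
- **Precision.** The standard error grows by 1/√(1 − correlation²): 1.05, 1.15 and 1.67 at 0.3, 0.5 and 0.8. Power falls from 99% to 98 / 96 / 80% with one degree of freedom, or 97 / 95 / 78% with six.
- **Missing covariates.** Table 5 marks implant, lead and generator details, as well as the X-ray, for collection where available. If 10% / 20% of subjects lack an item, complete-case power with six degrees of freedom is 96 / 94% at correlation 0.3, 93 / 90% at 0.5 and 74 / 70% at 0.8.
- **Extra noise variables.** With about 19 characteristics listed, a 20% screen would admit up to 19 × 0.20 = 3.8 irrelevant ones on average, against 19 × 0.05 = 0.95 at 5%.
- **Limits.** The fixed set does not help with a confounder left off it.
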